4.4 Early Withdrawal of Subjects

4.4.1 When and How to Withdraw Subjects

Subjects who do not complete the study protocol will be considered to have prematurely discontinued the study. The reasons for premature discontinuation (for example, voluntary withdrawal, toxicity, death) must be recorded on the case report form (CRF). Final study evaluations will be completed at the time of discontinuation. Reasons for withdrawal include, but are not limited to, the following:

1. Inter-current illness that would, in the judgment of the investigator, affect assessments of clinical status to a significant degree or require discontinuation of study drugs;
2. Unacceptable toxicity: Patients will be followed until resolution or stabilization;
3. Disease progression;
4. Withdrawal of patient consent;
5. Patient opting out of further treatment in the absence of progressive disease or significant comorbidity but still willing to have follow up regarding disease status;
6. Treatment delay greater than four weeks beyond the schedule for any toxicity
7. Non- compliance with study procedures that cannot be resolved;
8. Major protocol violations, including, but not limited to:
 1. failure to meet inclusion/exclusion criteria;
 2. failure to complete evaluations as required by protocol;
 3. use of concomitant therapies other than specified above.

The reason(s) for withdrawal should be noted in the case report form and in the patient's medical record. Standard supportive therapy should be maintained for subjects withdrawn from active treatment. Long-term follow-up data, including survival and progression data, will be collected.

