Hypophysitis	2-4	Toxicity resolves to Grade 0-1. Therapy with pembrolizumab can be continued while endocrine replacement therapy is instituted	Toxicity does not resolve within 12 weeks of last dose or inability to reduce corticosteroid to 10 mg or less of prednisone or equivalent per day within 12 weeks
Hyperthyroidism	3	Toxicity resolves to Grade 0-1	Toxicity does not resolve within 12 weeks of last dose or inability to reduce corticosteroid to 10 mg or less of prednisone or equivalent per day within 12 weeks
	4	Permanently discontinue	Permanently discontinue
Hypothyroidism		Therapy with pembrolizumab can be continued while thyroid replacement therapy is instituted	Therapy with pembrolizumab can be continued while thyroid replacement therapy is instituted
Infusion Reaction	2 ^b	Toxicity resolves to Grade 0-1	Permanently discontinue if toxicity develops despite adequate premedication
	3-4	Permanently discontinue	Permanently discontinue

Phase II Pembrolizumab Reirradiation

Toxicity	Hold Treatment For Grade	Timing for Restarting Treatment	Treatment Discontinuation
Pneumonitis	2	Toxicity resolves to Grade 0-1	Toxicity does not resolve within 12 weeks of last dose or inability to reduce corticosteroid to 10 mg or less of prednisone or equivalent per day within 12 weeks
	3-4	Permanently discontinue	Permanently discontinue
Renal Failure or Nephritis	2	Toxicity resolves to Grade 0-1	Toxicity does not resolve within 12 weeks of last dose or inability to reduce corticosteroid to 10 mg or less of prednisone or equivalent per day within 12 weeks
	3-4	Permanently discontinue	Permanently discontinue
All Other Drug-Related Toxicity ^c	3 or Severe	Toxicity resolves to Grade 0-1	Toxicity does not resolve within 12 weeks of last dose or inability to reduce corticosteroid to 10 mg or less of prednisone or equivalent per day within 12 weeks
	4	Permanently discontinue	Permanently discontinue

Note: Permanently discontinue for any severe or Grade 3 drug-related AE that recurs or any life-threatening event.

^a For patients with liver metastasis who begin treatment with Grade 2 AST or ALT, if AST or ALT increases by greater than or equal to 50% relative to baseline and lasts for at least 1 week then patients should be discontinued.

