^b If symptoms resolve within one hour of stopping drug infusion, the infusion may be restarted at 50% of the original infusion rate (e.g., from 100 mL/hr to 50 mL/hr). Otherwise dosing will be held until symptoms resolve and the subject should be premedicated for the next scheduled dose; Refer to Infusion Treatment Guidelines for further management details.

^c Patients with intolerable or persistent Grade 2 drug-related AE may hold study medication at physician discretion. Permanently discontinue study drug for persistent Grade 2 adverse reactions for which treatment with study drug has been held, that do not recover to Grade 0-1 within 12 weeks of the last dose.

Dosing interruptions are permitted in the case of medical / surgical events or logistical reasons not related to study therapy (e.g., elective surgery, unrelated medical events, patient vacation, and/or holidays). Subjects should be placed back on study therapy within 3 weeks of the scheduled interruption, unless otherwise discussed with the Sponsor. The reason for interruption should be documented in the patient's study record.

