5.4 Subject Compliance Monitoring

The study team will track subject compliance with the treatment regimen at each visit and note the dose, date, and time of study medication administration on the case report form. If there are any significant irregularities in compliance (in the opinion of the investigator), the subject should be withdrawn from the study. Interruptions from the protocol specified treatment plan for greater than 12 weeks between Pembrolizumab doses due to toxicity will require consultation between the investigator and the medical monitor and written documentation of the collaborative decision on subject management.

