Grade 3 and Grade 4	Withhold Pembrolizumab Discontinue if unable to reduce corticosteroid dose to < 10 mg per day prednisone equivalent within 12 weeks of toxicity	Systemic corticosteroids are indicated in addition to appropriate symptomatic treatment. May utilize 1 to 2 mg/kg prednisone or equivalent per day. Steroid taper should be considered once symptoms improve to Grade 1 or less and tapered over at least 4 weeks.

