5.6.1.2 Supportive Care Guidelines for Pneumonitis

Subjects with symptomatic pneumonitis should immediately stop receiving Pembrolizumab and have an evaluation. The evaluation may include bronchoscopy and pulmonary function tests to rule out other causes such as infection. If the subject is determined to have study drug associated pneumonitis, the suggested treatment plan is detailed in Table 5.

Table 5: Recommended Approach to Managing Pneumonitis

Study drug associated pneumonitis	Withhold/Discontinue Pembrolizumab?	Supportive Care
Grade 1 (asymptomatic)	No action	Intervention not indicated
Grade 2	Withhold Pembrolizumab, may resume treatment if improves to Grade 1 or resolves within 12 weeks	Systemic corticosteroids are indicated. Taper if necessary.

Phase II Pembrolizumab Reirradiation

Grade 3 and Grade 4	Permanently discontinue Pembrolizumab	Systemic corticosteroids are indicated. The use of infliximab may be indicated as appropriate.
---------------------	---------------------------------------	--

For Grade 2 pneumonitis that improves to \leq Grade 1 within 12 weeks, the following rules should apply:

- First episode of pneumonitis
 - May increase dosing interval by one week in subsequent cycles
- Second episode of pneumonitis – permanently discontinue Pembrolizumab if upon rechallenge subject develops pneumonitis \geq Grade 2

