5.8 Subject Withdrawal/Discontinuation Criteria

Subjects may withdraw consent at any time for any reason or be dropped from the trial at the discretion of the investigator should any untoward effect occur. In addition, a subject may be withdrawn by the investigator or the Sponsor if enrollment into the trial is inappropriate, the trial plan is violated, or for administrative and/or other safety reasons.

A subject must be discontinued from the trial for any of the following reasons:

- Withdrawal of consent.
- Confirmed radiographic disease progression

Note: A subject may be granted an exception to continue on treatment with confirmed radiographic progression if clinically stable or clinically improved, as consistent with irRC.

- Unacceptable adverse experiences or toxicities
- Intercurrent illness that prevents further administration of treatment
- Investigator's decision to withdraw the subject
- Confirmed positive serum pregnancy test and unwillingness to abort pregnancy
- Noncompliance with trial treatment or procedure requirements
- Loss to follow-up
- Completion of 17 cycles (about 12 months) of treatment with Pembrolizumab
- Other Administrative reasons

The End of Treatment and Follow-up visit procedures are listed in Section 7 (Protocol Flow Chart). After the end of treatment, each subject will be followed for 30 days for adverse event monitoring (serious adverse events will be collected for 90 days after the end of treatment). Subjects who discontinue for reasons other than progressive disease will have post-treatment follow-up for disease status until disease progression, initiation of non-study cancer treatment, withdrawal of consent or loss to follow-up. After documented disease progression each, subject will be followed by telephone or chart review for overall survival until death, withdrawal of consent, or the end of the study, whichever occurs first. All subsequent therapies will be recorded, if feasible.

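### For a Grade 4 immune-related event without its own dose-modification row, Table 4 says withhold where the Dose Modification Guidelines table says stop permanently; a four-week item in 4.4.1 also sits below the 12-week limits used elsewhere

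*Combined protocol and SAP*

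**What the plan says.** **Grade 4 immune-related events.**

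- The Dose Modification Guidelines table in 5.2 (labelled Table 1) has a catch-all row for drug-related toxicities that have no row of their own. It holds treatment at Grade 3 or severe and stops it permanently at Grade 4. The note under the table adds: "Permanently discontinue for any severe or Grade 3 drug-related AE that recurs or any life-threatening event". Table 8 in 8.2.4 defines Grade 4 as life threatening.
- Section 5.6.1.1 offers Table 4 for immune-related events not covered elsewhere in the protocol. It also refers to an irAE guidance document, said to be appended, which is not in the reviewed text. Table 4's last row covers Grades 3 and 4 together: "Withhold Pembrolizumab Discontinue if unable to reduce corticosteroid dose to < 10 mg per day prednisone equivalent within 12 weeks of toxicity".
- A note in 5.6.1 sends the reader to Section 5.2.1 for dose modification.

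**Length of a toxicity delay.**

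- Section 4.4.1 item 6 gives as a withdrawal reason: "Treatment delay greater than four weeks beyond the schedule for any toxicity". The list opens with "Reasons for withdrawal include, but are not limited to, the following".
- Section 5.8 has a separate compulsory list, headed "A subject must be discontinued from the trial for any of the following reasons", with no four-week item.
- Most held-toxicity rows of the Dose Modification Guidelines table discontinue only if recovery takes longer than 12 weeks from the last dose. Footnote c applies the same limit to persistent Grade 2 reactions that "do not recover to Grade 0-1 within 12 weeks of the last dose". Table 5 in 5.6.1.2 says of Grade 2 pneumonitis: "Withhold Pembrolizumab, may resume treatment if improves to Grade 1 or resolves within 12 weeks".
- Section 5.4, repeated in 8.1.1.6, says: "Interruptions from the protocol specified treatment plan for greater than 12 weeks between Pembrolizumab doses due to toxicity will require consultation".

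**The concern.** A clinician facing a Grade 4 immune-related event finds two dosing columns that do not agree. One ends pembrolizumab for good. The other pauses it and attaches discontinuation to a single condition, failure to bring the steroid dose down. What is at stake is possible re-exposure after a life-threatening event, and different handling of the same event from one patient to the next.

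The delay limits raise a smaller problem in the opposite direction: a patient whom the dosing rules would let restart may already meet a listed reason for withdrawal.

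**Working it through.** The plan states no figure on this point, so the check compares the rules and puts the two delay limits on one clock.

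**Step 1. Do the two tables cover the same events?** The catch-all row takes any drug-related toxicity without its own row. Table 4 takes immune-related events not detailed elsewhere. A drug-related immune event with no row of its own falls within the wording of both. Uveitis is an example: it is one of the seven pre-specified events of clinical interest in 3.1, and the only one of the seven with no row. Events with their own row are outside this point.

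**Step 2. Compare the dosing instruction by grade for such an event.**

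| Grade | Dose Modification Guidelines table (5.2) | Table 4 (5.6.1.1) | Agree? |
|---|---|---|---|
| 2 | Optional hold (footnote c) | Optional hold | Yes |
| 3 | Hold; 12-week limits on recovery and steroid reduction; stop if it recurs | Withhold; 12-week limit on steroid reduction | Broadly |
| 4 | Permanent stop (row and note) | Withhold; discontinue if steroids cannot be reduced in 12 weeks | No |

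The clear break is at Grade 4. Table 5, whose column has the same heading, states a permanent stop outright for Grades 3 and 4. A reader will therefore not take the word withhold in Table 4 to mean a permanent stop.

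**Step 3. Is there a rule of precedence?** None is stated. The pointer in 5.6.1 suggests that the dose-modification rules govern, but the body text has no Section 5.2.1, and the dose-modification heading inside 5.2 is unnumbered. The infusion-reaction table in 5.6.1 is also labelled Table 1, so the table number alone does not identify the governing table.

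**Step 4. Delay limits, in days since the last dose.** Inputs: 21-day cycle (5.2); four weeks beyond schedule (4.4.1 item 6); 12 weeks between doses (5.4 and 8.1.1.6).

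- Item 6 is met after day 21 + 4 × 7 = 49.
- Consultation is required after day 12 × 7 = 84.
- Span in which item 6 is met but consultation is not yet required: days 50 to 84, that is 84 − 49 = 35 days.

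The 12 weeks in the dose-modification table and Table 5 limit time to recovery, not the gap between doses. They show the time scale the dosing rules work to, but they do not enter this subtraction.

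**The case against.** **On Grade 4.** The dose-modification table is introduced in mandatory terms. Table 4 sits under suggested supportive care and is confined to events not detailed elsewhere. One can argue that the catch-all row and its note already detail the Grade 4 stop, leaving Table 4 to supply the lower-grade approach and the steroid advice. That is a reasonable reading and probably the intended one. Three safeguards also apply: immediate Sponsor discussion of Grade 2 or higher immune-related events (5.6.1.1), advance approval of rechallenge after a serious event under the dose-modification guidelines (Table 8), and reporting of Grade 3 or higher events to the DSMC within five business days (8.2). These lower the risk. They do not remove a dosing entry that differs from the other table, and the intended precedence has to be inferred because the pointer fails.

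A reader might infer that Table 4 authorises restart after a Grade 4 event. It does not say so; restart is only implied by withholding with a conditional stop. The unseen irAE guidance document may also address uveitis.

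**On the delay.** A reader might infer that 4.4.1 compels withdrawal after four weeks. The documents do not support that: the list is open, it is not worded as compulsory, and 5.8 omits the item and already allows withdrawal by investigator decision. Nor does 5.4 promise restart before 12 weeks. A reader might also infer that all dosing rules use 12 weeks. The diabetes/hyperglycemia, hypothyroidism and infusion-reaction rows carry no such limit. The 35 days should not be turned into a share of restarts, because the protocol does not fix the days on which a delayed dose may be given. What stands is that item 6 and the dosing rules send different signals over that span.

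**Conclusion.** Both inconsistencies are in the text, and they are not of equal weight.

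The main point is Grade 4. For drug-related immune events without their own row, one table stops pembrolizumab permanently and the other withholds it, with no working statement of which governs. This is a safety-relevant wording error. The documents give no expected number of such events, so its size can only be described by scope: one of seven pre-specified event categories, plus any other immune event without a row.

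The secondary point is the delay limit. The rules diverge over 35 days (days 50 to 84), assuming the nominal 21-day cycle. It is softer because item 6 is not mandatory.

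A reader might infer damage to the primary result. The documents do not support that. Under 4.4.2 all patients are followed for PFS and OS, and under 9.3.2 the primary analysis includes every enrolled patient whether or not pembrolizumab is given.

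**What to change.** 1. Split the last row of Table 4. Grade 3 keeps the present text; Grade 4 reads: *Permanently discontinue Pembrolizumab*.
2. Change the pointer in 5.6.1 to *Section 5.2, Dose Modification Guidelines table*, using the title because two tables carry the number 1.
3. State in 5.2 that this table governs dosing where Table 4 differs from it. Do not extend the sentence to 5.4 or 8.1.1.6, so that the consultation route beyond 12 weeks is kept.
4. Reword 4.4.1 item 6 to: *Toxicity that meets a discontinuation criterion in the Dose Modification Guidelines table, or a toxicity interruption of more than 12 weeks between doses unless continuation is agreed under Section 5.4*. The second clause keeps a time trigger for toxicities whose row has no limit, such as diabetes/hyperglycemia.
5. Check the irAE guidance document against the amended Table 4.

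The cost is a wording amendment: one table row, one cross-reference, one sentence and one list item. Sample size, analysis and visits do not change.

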5.6.1.2 Supportive Care Guidelines for Pneumonitis

Subjects with symptomatic pneumonitis should immediately stop receiving Pembrolizumab and have an evaluation. The evaluation may include bronchoscopy and pulmonary function tests to rule out other causes such as infection. If the subject is determined to have study drug associated pneumonitis, the suggested treatment plan is detailed in Table 5.

Table 5: Recommended Approach to Managing Pneumonitis

Study drug associated pneumonitis	Withhold/Discontinue Pembrolizumab?	Supportive Care
Grade 1 (asymptomatic)	No action	Intervention not indicated
Grade 2	Withhold Pembrolizumab, may resume treatment if improves to Grade 1 or resolves within 12 weeks	Systemic corticosteroids are indicated. Taper if necessary.

Phase II Pembrolizumab Reirradiation

Grade 3 and Grade 4	Permanently discontinue Pembrolizumab	Systemic corticosteroids are indicated. The use of infliximab may be indicated as appropriate.
---------------------	---------------------------------------	--

For Grade 2 pneumonitis that improves to \leq Grade 1 within 12 weeks, the following rules should apply:

- First episode of pneumonitis
 - May increase dosing interval by one week in subsequent cycles
- Second episode of pneumonitis – permanently discontinue Pembrolizumab if upon rechallenge subject develops pneumonitis \geq Grade 2

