5.2 Treatment Regimen

Patients will be treated with reirradiation with or without standard concurrent chemotherapy to all gross disease with proton beam therapy. The intended radiation dose should be at least 60 Gy of reirradiation in 1.8-2.0 Gy fractions with or without concurrent chemotherapy or in 4.0 Gy fractions without chemotherapy, at the provider's discretion. This corresponds to daily fractionated radiation over a period of approximately 3-8 weeks. The decision to use concurrent chemotherapy, and which regimen to utilize, are left to the discretion of the treating oncologist. The chemotherapy regimen and doses will be recorded in the patient record.

Pembrolizumab will be started 4 to 12 weeks after completion of reirradiation. Pembrolizumab will be given at a dose of 200 mg intravenously approximately every 21 days for 17 cycles (about 12 months) if there is no evidence of progressive disease or intolerable side effects.

Dose Modifications (Escalation/Titration/Other)

Adverse events (both non-serious and serious) associated with pembrolizumab exposure may represent an immunologic etiology. These adverse events may occur shortly after the first dose or several months after the last dose of treatment. Pembrolizumab must be withheld for drug-related toxicities and severe or life-threatening AEs as per 3 below. See Section 5.6 for supportive care guidelines, including use of corticosteroids.

Table 1: Dose Modification Guidelines for Drug-Related Adverse Events

Toxicity	Hold Treatment For Grade	Timing for Restarting Treatment	Treatment Discontinuation
Diarrhea/Colitis	2-3	Toxicity resolves to Grade 0-1	Toxicity does not resolve within 12 weeks of last dose or inability to reduce corticosteroid to 10 mg or less of prednisone or equivalent per day within 12 weeks
	4	Permanently discontinue	Permanently discontinue
AST, ALT, or Increased Bilirubin	2	Toxicity resolves to Grade 0-1	Toxicity does not resolve within 12 weeks of last dose
	3-4	Permanently discontinue (see exception below) ^a	Permanently discontinue
Type 1 diabetes mellitus (if new onset) or Hyperglycemia	T1DM or 3-4	Hold pembrolizumab for new onset Type 1 diabetes mellitus or Grade 3-4 hyperglycemia associated with evidence of beta cell failure	Resume pembrolizumab when patients are clinically and metabolically stable

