5.3 Preparation and Administration of Study Drugs

A research supply of Pembrolizumab will be supplied by Merck. It will be shipped to, stored and dispensed from Investigational Drug Services (IDS) of the Hospital of the University of Pennsylvania and Penn Presbyterian Medical Center for patients enrolled at that site. The drug preparation will be done in the pharmacy.

The investigator shall take responsibility for and shall take all steps to maintain appropriate records and ensure appropriate supply, storage, handling, distribution and usage of investigational product in accordance with the protocol and any applicable laws and regulations.

Clinical Supplies will be provided by Merck as summarized in Table 2.

Table 2: Product Descriptions

Product Name and Potency	Dosage Form
Pembrolizumab 100 mg/4mL	Solution for injection

Study Medication Administration

Pembrolizumab will be administered as a 30 minute intravenous infusion (treatment cycle intervals may be increased due to toxicity as described in Table 1). Sites should make every effort to target infusion timing to be as close to 30 minutes as possible. However, given the variability of infusion pumps from site to site, a window of -5 minutes and +10 minutes is permitted (i.e., infusion time is 30 minutes: -5 min/+10 min).

Phase II Pembrolizumab Reirradiation

Pembrolizumab Premedication

Patients do not require premedication prior to Pembrolizumab administration, as hypersensitivity reactions are rare.

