Subjects should receive appropriate supportive care measures as deemed necessary by the treating investigator. Suggested supportive care measures for the management of adverse events with potential immunologic etiology are outlined below. Where appropriate, these guidelines include the use of oral or intravenous treatment with corticosteroids as well as additional anti-inflammatory agents if symptoms do not improve with administration of corticosteroids. Note that several courses of steroid tapering may be necessary as symptoms may worsen when the steroid dose is decreased. For each disorder, attempts should be made to rule out other causes such as metastatic disease or bacterial or viral infection, which might require additional supportive care. The treatment guidelines are intended to be applied when the investigator determines the events to be related to pembrolizumab.

Note: if after the evaluation the event is determined not to be related, the investigator does not need to follow the treatment guidance (as outlined below). Refer to Section 5.2.1 for dose modification.

It may be necessary to perform conditional procedures such as bronchoscopy, endoscopy, or skin photography as part of evaluation of the event.

- **Pneumonitis:**
 - For **Grade 2 events**, treat with systemic corticosteroids. When symptoms improve to Grade 1 or less, steroid taper should be started and continued over no less than 4 weeks.
 - For **Grade 3-4 events**, immediately treat with intravenous steroids. Administer additional anti-inflammatory measures, as needed.
 - Add prophylactic antibiotics for opportunistic infections in the case of prolonged steroid administration.
- **Diarrhea/Colitis:**

Subjects should be carefully monitored for signs and symptoms of enterocolitis (such as diarrhea, abdominal pain, blood or mucus in stool, with or without fever) and of bowel perforation (such as peritoneal signs and ileus).

 - All subjects who experience diarrhea/colitis should be advised to drink liberal quantities of clear fluids. If sufficient oral fluid intake is not feasible, fluid and electrolytes should be substituted via IV infusion. For Grade 2 or higher diarrhea, consider GI consultation and endoscopy to confirm or rule out colitis.
 - For **Grade 2 diarrhea/colitis**, administer oral corticosteroids.
 - For **Grade 3 or 4 diarrhea/colitis**, treat with intravenous steroids followed by high dose oral steroids.

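### The pneumonitis instructions in Sections 5.2, 5.6.1 and 5.6.1.2 are not aligned on recurrence, taper and steroids at resumption, and no passage says which governs

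*Combined protocol and SAP*

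**What the plan says.** The dose-modification table in Section 5.2 is introduced with mandatory wording: "Pembrolizumab must be withheld for drug-related toxicities and severe or life-threatening AEs as per 3 below". Its pneumonitis row holds treatment at Grade 2 and gives the restart condition as "Toxicity resolves to Grade 0-1". For Grade 2 it names two reasons to discontinue. One is failure to resolve within 12 weeks of the last dose. The other is "inability to reduce corticosteroid to 10 mg or less of prednisone or equivalent per day within 12 weeks". Grades 3 and 4 stop treatment permanently. The note under the table holds its only recurrence rule: "Permanently discontinue for any severe or Grade 3 drug-related AE that recurs or any life-threatening event".

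The pneumonitis bullets in Section 5.6.1 call for systemic steroids at Grade 2, and then: "When symptoms improve to Grade 1 or less, steroid taper should be started and continued over no less than 4 weeks".

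Section 5.6.1.2 presents Table 5 as a suggested plan. At Grade 2, pembrolizumab is withheld and may resume if the event falls to Grade 1 or resolves within 12 weeks. The supportive-care cell reads "Systemic corticosteroids are indicated. Taper if necessary". Below the table, rules for Grade 2 events that improve in time say that at a second episode the site is to "permanently discontinue Pembrolizumab if upon rechallenge subject develops pneumonitis" of Grade 2 or higher.

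Section 5.3, on dosing intervals, sends the reader to the dose-modification table: "treatment cycle intervals may be increased due to toxicity as described in Table 1". Section 5.6.1 sends the reader to a Section 5.2.1 for dose modification.

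**The concern.** Someone managing a pneumonitis event will probably open one of these places, not all three. What that person then does about a second Grade 2 episode, the length of the taper, and steroid dose at resumption depends on which one it was. The text with the firmest wording, to which other sections point, is the one that lacks the second-episode rule.

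This matters more than an ordinary wording slip. Grade 2 or higher pneumonitis is one of the seven adverse events of clinical interest pre-specified in Section 3.1. Every patient has had thoracic reirradiation before pembrolizumab. Section 8.1.5.3 bars the start of pembrolizumab on pneumonitis grounds only when it is symptomatic and Grade 3 or higher. Toxicity is a secondary endpoint (Section 3.3). Uneven rechallenge would therefore bear on patient safety and on how the reported recurrence, discontinuation and exposure figures are read.

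**Working it through.** The protocol states no figure on this point, and no arithmetic applies. The check is a comparison of the three texts, item by item.

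**Second Grade 2 episode**
- Section 5.2 table: the Grade 2 row is not limited to a first episode. Recurrence is not among its reasons to discontinue, and the note on recurrence covers severe or Grade 3 events, plus any life-threatening event. The table therefore says nothing specific about a second Grade 2 pneumonitis. A reader who has only this table would apply the general row again: hold, then restart at Grade 0-1.
- Section 5.6.1 bullets: silent on recurrence.
- Section 5.6.1.2, below Table 5: permanent discontinuation if pneumonitis of Grade 2 or higher develops on rechallenge.
- Result: an express rule in one place and silence in the other two. The outcome differs if the Section 5.2 table is used alone.

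**Taper after Grade 2**
- Section 5.2 table: no taper instruction.
- Section 5.6.1 bullets: a taper is started on improvement and lasts at least 4 weeks.
- Table 5: taper only if needed.
- Result: a direct difference for the same grade of the same event, between Section 5.6.1 and Table 5.

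**Steroids and timing at resumption**
- Section 5.2 table: not getting down to 10 mg per day of prednisone equivalent within 12 weeks is a reason to discontinue. Non-resolution is counted over 12 weeks from the last dose.
- Table 5: resumption depends on grade alone, and its 12 weeks has no stated starting point.
- Result: a condition present in one text and missing from the other, and a window anchored in one and not in the other.

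**Which text governs**
- No passage gives an order of precedence. The Section 5.2 table is introduced as mandatory; Table 5 is introduced as suggested and titled as recommended, although the rules beneath it are said to apply.
- The cross-references do not help. Section 5.6.1 points to Section 5.2.1, which has no heading in the available text. The lead-in to the Section 5.2 table points to an item 3 that cannot be identified. The label Table 1 is used twice, for dose modification in Section 5.2 and for infusion reactions in Section 5.6.1.

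**The case against.** The strongest reply is that a general row and a specific rule do not conflict. The Section 5.2 table does not tell anyone to rechallenge after a second Grade 2 pneumonitis; it simply does not address that case. The rule under Table 5 does. Stopping permanently breaks no sentence of the Section 5.2 table, while rechallenge departs from Section 5.6.1.2. This stands. A reader might infer that the two tables give opposite orders, or that a site could comply with the protocol by either course. The protocol read as a whole does not support either inference.

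The reply does not remove the point. Nothing tells the reader that the specific text prevails, and the difference in force of wording points the other way. Applied to the other two items, the same principle would set aside the 4-week taper and the steroid condition, and nothing suggests that was intended.

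Other parts of the reply also have weight:
- The steroid texts can be followed together, since Table 5 only permits resumption and Section 5.2 adds a reason to discontinue. Section 5.5.2 also restricts glucocorticoid use. This item is an omission in Table 5, not a contradiction.
- A reader might see a further conflict over dosing intervals, because Section 5.3 refers to Table 1 while the one-week increase appears only under Table 5. The documents do not bear this out. Section 5.3 is permissive, holding a dose under the Section 5.2 table itself lengthens the interval, and Section 8.1.2.6 anticipates extended cycle frequencies. The 3-day allowance in the flow chart is a scheduling window.
- Safeguards exist. Section 5.6.1.1 asks that immune-related events of Grade 2 or higher be discussed with the sponsor at once, a medical monitor is appointed (Section 8.2), and this is a single-center trial. These lower the chance of uneven handling but supply no single rule to apply.

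**Conclusion.** The point holds as an inconsistency in wording with a bearing on patient safety. Section 5.2, Section 5.6.1 and Section 5.6.1.2 differ on taper, one of them omits the steroid condition and the start of the 12-week window, and only one carries the second-episode rule. No passage ranks them. The conclusion rests on the text alone.

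Its size cannot be put in patients. The documents give no rate for a first Grade 2 pneumonitis or for recurrence on rechallenge, so any count would only reflect assumed rates. Nor would every patient with Grade 2 pneumonitis meet the steroid difference: it matters only for someone who reaches Grade 1 or less within 12 weeks but cannot get down to 10 mg or less.

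The population for the primary analysis is not affected. Sections 9.3 and 9.3.2 include patients in the progression-free survival analysis whether or not pembrolizumab was given. The exposure is in clinical management and in the secondary toxicity results. The passages should be reconciled; this review takes no position on which clinical rule is right.

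**What to change.** - Write one pneumonitis rule and use it in all three places: the Section 5.2 table, the Section 5.6.1 bullets, and Table 5 with its rules. It should cover a second Grade 2 episode, steroid status at resumption, the taper, and the starting point of the 12 weeks. The sponsor and medical monitor decide the content.
- State which text governs if any difference remains.
- Correct the pointers: the reference to Section 5.2.1, the reference to item 3 in the lead-in to the Section 5.2 table, and the duplicate Table 1 label, which also makes the reference in Section 5.3 ambiguous.
- At the same time, check the rule against the other texts on toxicity delays. Section 4.4.1 lists a delay of more than four weeks beyond schedule as a reason for withdrawal. Sections 5.4 and 8.1.1.6 send interruptions of more than 12 weeks to a consultation.

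The cost is a protocol wording amendment and a memo to site staff. It adds no procedures, visits or patients.
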